## PROTOCOL

Neurosteroids as Novel Therapeutic Agents for PTSD in OEF/OIF/OND Veterans

PI: [name], PhD

preliminary data in OEF/OIF/OND Veterans, treatment with DHEA has potential as a safe, effective, well tolerated, immediately accessible, and inexpensive treatment for PTSD and multiple associated symptom domains.

### Design

This is a parallel-group, double-blind, placebo (PBO)-controlled, randomized Phase 2 pilot study using adjunctive dehydroxyepiandrosterone [DHEA (400 mg)] will be evaluated to establish Proof of Concept (POC) for this agent in OEF/OIF/OND Veterans with PTSD.

Aim 1. To determine the effects of an acute oral administration of adjunctive DHEA (400 mg) on neuroimaging measures of functional connectivity. We will conduct a parallel-group, double-blind, placebo (PBO)-controlled, randomized Phase 2 pilot study with one-time oral DHEA 400 mg in target engagement. To establish POC, we seek to determine if DHEA is superior to PBO in target engagement of neural circuits related to fear-anxiety-emotion regulation using the shifted-attention emotion appraisal (SEAT) paradigm (see below). Following a two-week placebo lead-in period (all participants), subjects will be randomized to receive a one-time oral dose of adjunctive DHEA (400mg) or PBO. Neuroimaging will occur 2 hours following drug administration for peak level effects on target engagement of fear-anxiety emotion circuit connectivity, as previously conducted by Sripada, [name], [name] et al.).

Primary Outcome Measure The primary outcome measure will be functional connectivity between amygdala-hippocampus assessed using fMRI based SEAT Paradigm as a target engagement endpoint. The fMRI based SEAT Paradigm has been previously validated to an acute administration of DHEA (400 mg) in healthy volunteers by members of my career development team, Drs. [name] and [name] (Sripada et al., 2013).

Aim 2. To evaluate a sustained 6-week adjunctive DHEA treatment compared to PBO on PTSD symptoms severity (CAPS-5), co-occurring depression (BDI), and other secondary outcome measures such as resilience (CD-RISC). Following randomization to acute DHEA administration or PBO the subject will continue to receive study drug for 6 weeks (for DHEA, fixed escalating doses: 100 mg per day in divided doses x 1 week, followed by 200 mg per day in divided doses x 1 week, followed by 400 mg per day in divided doses x 4 weeks).

### Secondary Outcome Measures

Secondary outcome measures will include: Change in the Clinician-Administered PTSD Scale for DSM-5 (CAPS-5). The CAPS-5 is a structured interview for assessing PTSD diagnostic status and symptom severity. The clinical coordinators in our research group have been trained in the administration of the CAPS by [name]. We will use a threshold of  $\geq 33$  on the CAPS-5, consistent with recently reported pharmacological intervention studies in Veterans with combat PTSD (Sullivan et al

## PROTOCOL

Neurosteroids as Novel Therapeutic Agents for PTSD in OEF/OIF/OND Veterans  
PI: [name], PhD

2016; ACNP annual meeting). Depression symptoms (as assessed with the Beck-Depression Inventory (II), HAM-D, and NIH derived PROMIS scales for depression; anxiety symptoms, as assessed by the HAM-A and PROMIS-Anxiety scale; overall assessment of psychological functioning, as assessed by the SCL-90R CGI component; pain symptoms, as assessed by the PROMIS-Pain Intensity scale and Brief Pain Inventory (BPI); sleep disturbance, as assessed by the PROMIS-Sleep Disturbance scale; anger, as assessed by the PROMIS-Anger scale; impulsivity as assessed by the Barrat Impulsivity Scale (BIS-11) and resilience, as assessed by the Connor-Davidson Resilience Scale (CD-RISC).

Aim 3. To determine the metabolic profile of DHEA in order to identify specific downstream neurosteroid alterations that may contribute to its clinical effects using mass spectrometry based techniques. We will use highly sensitive and specific mass spectrometry-based technology for neurosteroid quantifications, as previously described and as outlined below. While neurosteroids such as DHEA and DHEAS have been measured in serum by immunoassay for many years, some high-impact journals are now requiring mass spectrometry approaches - and will no longer publish papers that utilize other methods such as immunoassay (as of January 1, 2015 for the *Journal of Clinical Endocrinology and Metabolism*). Thus, the reliable quantification of the neurosteroids proposed in this study requires mass spectrometry-based techniques. The PI's primary mentor, [name], has optimized and validated a highly sensitive and specific GC/MS method for quantifying neurosteroids (preceded by HPLC purification), and her laboratory will donate these mass spectrometry analyses for this CDA-II application. This equipment is located in her Durham VA laboratory and dedicated solely to neurosteroid analyses. [name] has conducted numerous clinical studies in which she has quantified neurosteroid profiles following pregnenolone administration, and determined that increases in neurosteroids post-treatment appear to be predictive of treatment response ([name] et al, 2016 – pregnenolone in mild TBI; [name] et al 2014 – neurosteroid intervention in schizophrenia; Brown et al 2014 –bipolar depression and pregnenolone; [name] et al 2009 – neurosteroid intervention in schizophrenia). We will conduct neurosteroid analyses in approximately 40 participants across 5 visits (approximately 400 neurosteroid assessments, although it is anticipated that there will be a 20% drop-out rate among the total of 40 participants who are randomized).

### Tertiary Outcome Measures

Tertiary outcome measures will include: Radioimmunoassay for Neurosteroid quantifications of serum levels of DHEA, DHEAS, and androsterone. These neurosteroids will be correlated with symptomatic rating scales.

Exploratory Aim: To investigate if treatment with DHEA impacts myelin integrity (as assessed by susceptibility tensor imaging/STI), and to examine myelin integrity as a possible biomarker for PTSD treatment response. We will also determine if serum neurosteroid levels are correlated with neuroimaging parameters utilizing STI (QSM)

## PROTOCOL

Neurosteroids as Novel Therapeutic Agents for PTSD in OEF/OIF/OND Veterans  
PI: [name], PhD

and fMRI. We estimate that approximately 80% of all participants enrolling in the proposed randomized controlled trial will also receive neuroimaging to an acute administration of DHEA or PBO placebo and post-treatment with DHEA or PBO. We thus anticipate that approximately 32 or more participants will undergo neuroimaging to an acute treatment with DHEA or PBO and at study completion (a minimum of approximately 16 participants per group in this pilot POC study). Susceptibility tensor imaging is a new methodology created by our collaborator at Duke, [name].

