### Exploratory Outcome Measures

The exploratory outcome measures will include: STI (myelin integrity); fMRI measures (amygdala and hippocampal connectivity); serum neurosteroid levels (DHEA; DHEAS; androsterone); PTSD symptom severity (CAPS-5); and other rating scale measures of co-occurring symptoms.

*Experimental Design:* The proposed design is a parallel-group, double-blind, PBO-controlled, randomized Phase 2 pilot study of adjunctive DHEA vs. PBO to determine target engagement of fear-anxiety-emotional circuit regulation and potential efficacy of DHEA in 40 OEF/OIF/OND Veterans with PTSD. Subjects will be randomized to receive a one-time oral dose of DHEA (400mg) or PBO and sustained administration of the study drug for 6 weeks. There will be a 2 week placebo lead-in period [all participants], followed by subjects continuing in the randomization block of DHEA or placebo for 6 weeks following acute administration. 40 subjects will be randomly assigned to one of two groups; assuming approximately a 20% drop-out rate, we anticipate that 32 participants will have at least one visit post-randomization and will be included in the statistical analysis plan (approximately 16 participants per group); a modified intent-to-treat approach will be utilized. The research pharmacist at the Durham VA will be responsible for randomization of participants in this study; a randomized block design will be utilized (4 participants).

*Shifted-Attention Emotion Appraisal (SEAT) Paradigm:* In order to investigate the brain basis of fear-anxiety emotional response and regulation, [name] laboratory has developed an emotion appraisal task (Klumpp et al, 2011; Sripada et al., 2013), modifying the task of Anderson et al (2003), and collaborating with [name] to evaluate the impact DHEA in healthy volunteers. My mentoring and collaborative team has thus demonstrated that the SEAT paradigm is an effective probe of neurosteroid regulatory effects (Sripada et al, 2013). The SEAT task uses compound stimuli that include emotional faces and neutral scenes. Stimuli include pictures of faces in front of buildings, as well as 20 pictures of faces or buildings alone. The face pictures represent neutral, angry, or fearful expressions, and the buildings are of indoor or outdoor portraits.

Participants are asked to respond to three different questions, in three different conditions: (1) 'Gender': whether the face is male or female; (2) 'Inside/Outside':

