### **Selection of Subjects**

Forty OEF/OIF/OND Veterans with PTSD between the ages of 18-65 will be randomized. Both male and female subjects and all ethnic groups will be eligible to participate in this study. All subjects will be currently experiencing PTSD, as evidenced by a CAPS-5 score that is  $\geq 33$  at baseline. We chose a CAPS-5 score of  $\geq 33$  after review of the available limited literature on this area. For example, a recent poster presented at the American College of Neuropsychopharmacology (ACNP) provided for rationale on use of CAPS-5 score of  $\geq 29$  for non-combat PTSD vs  $\geq 33$  for combat PTSD (Sullivan, G et al., 55th Annual Meeting; ACNP, December 7, 2016). We anticipate that a number of participants will have co-occurring depression symptoms and a history of mild TBI (mild TBI and major depression are not exclusionary); we will thus control for the presence of major depression and a history of mild TBI in the statistical analysis. Patients who have a history of moderate or severe TBI will be excluded. Veterans will be recruited from the Durham VA Medical Center and VA Mid-Atlantic MIRECC Repository and Post-deployment Health Study in OEF/OIF/OND Veterans. This Repository has enrolled over 3,200 OEF/OIF/OND Veterans to date, and

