#### Exclusion Criteria:

1. Unstable medical or neurological illness, including seizures, renal impairment or CVA and inability to participate in neuroimaging (fMRI).
2. Use of oral contraceptives or other hormonal supplements, as it is unclear if DHEA metabolism to other neurosteroids such as estradiol may potentially impact contraceptive efficacy.
3. Significant suicidal or homicidal ideation.
4. Current DSM-5 diagnosis of bipolar disorder, schizophrenia, or other psychotic disorder (including major depression with psychotic features), or cognitive disorder due to a general medical condition.
5. Female patients who are pregnant or breast-feeding.
6. Known allergy to study medication.
6. History of moderate or severe TBI.

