### Study Interventions

We will conduct a parallel-group, double-blind, placebo (PBO)-controlled, randomized Phase 2 pilot study with 400mg DHEA to test whether we can establish proof of concept (POC) for this agent. 40 OEF/OIF/OND Veterans with PTSD will be randomized to receive a one-time oral adjunctive treatment with DHEA or PBO in the fMRI paradigm (same day). Participants will then continue to receive a 6-week sustained treatment of DHEA or PBO. To establish POC, we seek to determine whether DHEA is superior to

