## PROTOCOL

Neurosteroids as Novel Therapeutic Agents for PTSD in OEF/OIF/OND Veterans  
PI: [name], PhD

specific absorption ate (SAR), time varying magnetic fields (dB/dt), and acoustic noise. If a subject has previously worked with metal, they will need a skull x-ray prior to the MRI scan. The skull x-ray involves a small amount of radiation. The radiation received in this x-ray is the same as from living in a high-altitude city such as Denver for 4 weeks, or taking 8 airplanes flights from New York to Los Angeles.

b) Emotional Distress: Participants may experience emotional distress because of participating in this study. The study procedures could potentially lead to emotional distress from discussing medical histories or deployment experiences. Being placed in an MRI machines can at times induce feeling associated with claustrophobia. Each participant will be closely monitored for emotional distress and emergent suicidal ideation and homicidal ideation at screening and each study visit (it is anticipated that this will be rare). If a participant becomes significantly distressed or if intervention is deemed appropriate, they will be escorted to the Durham VA Emergency Room for additional assessment.

c) Unauthorized Access to Data: There is a possibility of an unauthorized party gaining access to secure PHI contained in the database. This is also a low risk, and several precautions have been implemented to minimize unauthorized access. First, reports from participants' clinical records concerning research observations will not be made available to outside medical facilities without the written consent of the patients. All clinical biological data obtained from research interviews and the laboratory will be coded. The data will be kept in a locked file cabinets and accessible only to authorized research personnel. Only study numbers will appear on specimens, data and documents used for evaluation or statistical analysis. In addition, any publication resulting from this research will not identify individual participants.

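### The acute fMRI scan is the primary outcome, yet the plan expects imaging in only about 80% of participants, and it presents 32 scanned at completion as a minimum when its 20% drop-out makes 32 a ceiling

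*Combined protocol and SAP*

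**What the plan says.** Aim 1 (Design section) makes fMRI amygdala-hippocampus connectivity the primary outcome, imaged 2 hours after the randomised dose. Study Interventions says that the 40 Veterans "will be randomized to receive a one-time oral adjunctive treatment with DHEA or PBO in the fMRI paradigm (same day"). Exclusion criterion 1 includes "inability to participate in neuroimaging (fMRI"). The Schedule of Events places MRI at Weeks 2 and 8 and marks neither as optional.

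The Exploratory Aim describes imaging differently. It estimates that "approximately 80% of all participants enrolling in the proposed randomized controlled trial will also receive neuroimaging to an acute administration of DHEA", and the sentence runs on so that the same rate covers "neuroimaging to an acute administration of DHEA or PBO placebo and post-treatment with DHEA or PBO". From this it concludes that "approximately 32 or more participants will undergo neuroimaging to an acute treatment with DHEA or PBO and at study completion", and it describes about 16 per group as the minimum.

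Drop-out is stated elsewhere. The Experimental Design paragraph assumes about 20% and continues: "we anticipate that 32 participants will have at least one visit post-randomization and will be included in the statistical analysis plan". Data Analysis and Statistical Considerations prints 10% beside the same 32, defines the modified intent-to-treat set by having at least one post-randomisation visit, and takes n = 32 for power.

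**The concern.** A scan that supplies the primary outcome cannot also be something that only a subset receives. The three statements (all 40 dosed within the fMRI paradigm, exclusion of those who cannot be scanned, about 80% imaged) do not fit together unless the 80% refers to loss before the second scan, and the plan does not say so.

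Two things are at stake. First, Objective 1 can be answered only in people who have the acute scan. The analysis set is counted in visits, so a participant can belong to it without a primary outcome, and the fMRI analysis text does not say how a missing scan is handled. Second, the Week 8 imaging questions (connectivity after sustained treatment, myelin change) rest on a stated minimum of about 16 per group. That figure has the same value as the visit-based count of 32, although one counts scans at the end of treatment and the other counts people seen at least once after randomisation.

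**Working it through.** **Inputs**
- Randomised: 40 (Selection of Subjects: "Forty OEF/OIF/OND Veterans with PTSD between the ages of 18-65 will be randomized").
- Imaging rate: 80%, both scans jointly (Exploratory Aim).
- Drop-out before any post-randomisation visit: 20% (Experimental Design); 10% (Data Analysis and Statistical Considerations).
- Visits after randomisation at Week 2: Weeks 4, 6 and 8 (Schedule of Events).

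**1. The plan's own figure.** 40 x 0.80 = 32, or 16 per group. The stated number reproduces exactly from the rate in the preceding sentence.

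**2. Acute scan.** If 80% have both scans, at least 32 have the acute one, and at most 40 can. Missing primary outcomes therefore number between 40 - 40 = 0 and 40 - 32 = 8.
- At the 0 end, everyone is scanned acutely and all the loss falls before Week 8.
- At the 8 end, all the loss is at the acute scan.

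**3. Completion scan if the 80% is retention.** With 20% drop-out, 40 x 0.80 = 32 reach at least one post-randomisation visit. Completers cannot exceed this. Having 32 scanned at Week 8 needs no loss between the first such visit and Week 8, and a scan in every remaining participant. So 32 is the most that the 20% rate allows.

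**4. Completion scan if the 80% is imaging uptake, separate from drop-out.** The result depends on how far the two losses fall on the same people, which the plan does not state.

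| Assumption | Formula | Number at Week 8 |
|---|---|---|
| 20% drop-out, no overlap of losses | 40 x (0.8 + 0.8 - 1) | 24 |
| 20% drop-out, independent | 40 x 0.8 x 0.8 | 25.6 |
| 20% drop-out, full overlap | 40 x 0.8 | 32 |
| 10% drop-out, no overlap | 40 x (0.8 + 0.9 - 1) | 28 |
| 10% drop-out, independent | 40 x 0.8 x 0.9 | 28.8 |
| 10% drop-out, full overlap | 40 x 0.8 | 32 |

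No row exceeds 32, and all of them leave out any loss after the first post-randomisation visit.

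**5. Is 32 a minimum even on the plan's joint rate?** If each of 40 people independently has an 80% chance of both scans, the binomial probability of 32 or more is 0.59. So 32 is then an expected value, not a floor.

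**6. The two drop-out rates.** 40 x 0.90 = 36, not 32. The 10% figure does not produce the number printed beside it. If 10% were the intended rate, the ceiling from drop-out alone would be 36.

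**The case against.** The strongest reply is that the 80% is simply the complement of the 20% drop-out. It covers both scans, and the same 32 and 16 per group appear wherever drop-out is discussed. On that reading nearly everyone has the acute scan, the losses come later, and multiplying by 0.8 a second time counts them twice. This is a possible reading, and it rules out two stronger inferences. A reader might infer that 8 participants will lack the primary outcome; the text supports only a range of 0 to about 8. A reader might also infer that 32 is an arithmetic error and that about 26 (13 per group) is the true figure. That figure needs independent, compounding losses, which the documents never state.

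The reply does not remove the problem. The Exploratory Aim never calls its 80% retention, and the word *also* points to imaging in a subset. If it is retention, 32 at completion still equals the number seen at least once, with no allowance for later withdrawal, although the protocol provides for withdrawal during treatment.

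A second reply is that scan eligibility is already covered. Exclusion 1 exists, a study physician determines eligibility, medical history and physical examination come at Week 0, and the protocol states: "If a subject has previously worked with metal, they will need a skull x-ray prior to the MRI scan". This largely stands. The missing row in the schedule does not show that no check is made. What is lacking is a statement that the check is complete before randomisation rather than only before the scan.

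It is also fair that this is a pilot, that n = 32 is already the number taken for power, and that no power claim is made for Week 8 imaging.

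**Conclusion.** The concern holds as an inconsistency in the plan. The 80% imaging estimate conflicts with a primary outcome that needs the acute scan in every randomised participant and with an exclusion for those who cannot be scanned. As written, between 0 and about 8 of 40 could lack the primary outcome.

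The completion figure is correctly multiplied but wrongly described. Under 20% drop-out, 32 is an upper limit presented as a minimum. If the 80% is uptake separate from that drop-out, the number is 24 to 32 before any later loss.

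These ranges rest on 40 being the base for the 80%: the text speaks of participants enrolling, and no larger enrolled number is given. The effect on power cannot be computed, because no effect size, standard deviation or target power is stated. The documents do not establish that a scanned subset would be self-selected or that MRI screening is absent.

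**What to change.** - State that every randomised participant is to have the acute scan, and delete the 80% estimate as it applies to that scan.
- Confirm exclusion 1 before randomisation, within the existing two-week lead-in, including the metal history and any skull x-ray the protocol already requires.
- Say whether the 80% is imaging uptake or retention, and reconcile the 20% and 10% drop-out figures.
- Restate the Week 8 imaging number as at most about 32 (16 per group) under 20% drop-out, and remove the language that makes it a minimum.

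The cost is protocol wording and the timing of checks that the protocol already calls for. A few participants would be screened out before randomisation, and the Week 8 imaging figure would look less favourable.

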### Exploratory Outcome Measures

The exploratory outcome measures will include: STI (myelin integrity); fMRI measures (amygdala and hippocampal connectivity); serum neurosteroid levels (DHEA; DHEAS; androsterone); PTSD symptom severity (CAPS-5); and other rating scale measures of co-occurring symptoms.

*Experimental Design:* The proposed design is a parallel-group, double-blind, PBO-controlled, randomized Phase 2 pilot study of adjunctive DHEA vs. PBO to determine target engagement of fear-anxiety-emotional circuit regulation and potential efficacy of DHEA in 40 OEF/OIF/OND Veterans with PTSD. Subjects will be randomized to receive a one-time oral dose of DHEA (400mg) or PBO and sustained administration of the study drug for 6 weeks. There will be a 2 week placebo lead-in period [all participants], followed by subjects continuing in the randomization block of DHEA or placebo for 6 weeks following acute administration. 40 subjects will be randomly assigned to one of two groups; assuming approximately a 20% drop-out rate, we anticipate that 32 participants will have at least one visit post-randomization and will be included in the statistical analysis plan (approximately 16 participants per group); a modified intent-to-treat approach will be utilized. The research pharmacist at the Durham VA will be responsible for randomization of participants in this study; a randomized block design will be utilized (4 participants).

*Shifted-Attention Emotion Appraisal (SEAT) Paradigm:* In order to investigate the brain basis of fear-anxiety emotional response and regulation, [name] laboratory has developed an emotion appraisal task (Klumpp et al, 2011; Sripada et al., 2013), modifying the task of Anderson et al (2003), and collaborating with [name] to evaluate the impact DHEA in healthy volunteers. My mentoring and collaborative team has thus demonstrated that the SEAT paradigm is an effective probe of neurosteroid regulatory effects (Sripada et al, 2013). The SEAT task uses compound stimuli that include emotional faces and neutral scenes. Stimuli include pictures of faces in front of buildings, as well as 20 pictures of faces or buildings alone. The face pictures represent neutral, angry, or fearful expressions, and the buildings are of indoor or outdoor portraits.

Participants are asked to respond to three different questions, in three different conditions: (1) 'Gender': whether the face is male or female; (2) 'Inside/Outside':

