### 3. Potential Risks

a) *Physical Risk*: Physical risks associated with participation in this study include the risks of drawing blood and adverse effects from the study medication. Possible side effects from drawing blood include bruising, bleeding, or pain at the injection site, and (rarely) fainting and infection. Blood draws at each visit are minimal risk. In terms of the study medication, DHEA has been well-tolerated at doses up to 1,600mg per day over several weeks of administration. Side effects exceeding placebo that have occurred in previous clinical trials with DHEA have included mild acne, hirsutism, and decreased HDL levels. If a participant develops side effects at any dose, they may be brought down to the previously tolerated dose or they may be withdrawn from the study and, as by the PI or MD members of the research team (Drs. [name], [name], and [name]), referred for evaluation and treatment. We will perform laboratories at each study visit (Chem 7, CBC, GI Panel) and an ECG at study entry and completion. No serious adverse events have been reported to date utilizing DHEA (sold as a dietary supplement over-the-counter in the U.S.). Of note, participants will NOT be tapered from their current stable medication regimen; DHEA will only be “added on” to treatment-as-usual.

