### Treatment Compliance

Compliance for each visit interval is defined as taking between 80% and 100% of the study drug prescribed for that interval. For subjects who demonstrate noncompliance, the PI and/or study coordinator will counsel patients on the importance of study drug compliance and drug accountability.

The following procedures will be employed to assure appropriate drug accountability:  
-Drug accountability will be emphasized at the screening visit and throughout the clinical trial.  
-Drug accountability forms will be provided in the clinical trial records binder or similar file.

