### **Adverse Events**

This protocol presents minimal risks to participants. In the unlikely event than an adverse event occurs, serious and unanticipated and related adverse events or unanticipated problems involving risks to participants or others will be reported in writing within 48 hours to the IRB at the Durham VA Health Center and any appropriate funding and regulatory agencies. Adverse events will be recorded by administration of a side effect rating scale (Hillside Adverse Events Form) and reviewed by a study physician. Adverse events will be assessed at all study visits after the screening visit (i.e. Visits 2-5). In addition to receiving these regular adverse effect assessments, patients will be given a toll-free study number that they can call if they have questions regarding the dose escalation schedule or medication side effects. Participants will also be provided with the cell phone numbers of [name] and [name].

We will also summarize all adverse events (cumulative to date) in our reports to the FDA, Clinical Science Research & Development Central Data Monitoring Committee at Hines (CSR&D DMC), and annual request for continuing approval to the IRB. The principal investigator is responsible for monitoring the data, assuring protocol compliance, and conducting the safety reviews at intervals appropriate to the study. During the review process the principal investigator will evaluate whether the study should continue unchanged, require modification/amendment, continue or close to enrollment. Specifically, the principal investigator will assess whether the adverse event affects the Risk/Benefit ratio of the study and whether modifications to the protocol (at Risks to Subjects) or consent form (at Risk and Inconveniences) are required. The investigator will apprise fellow investigation and study personnel of all adverse events will be reported to the appropriate regulatory and oversight agencies in accordance with their reporting requirements and regulations.

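### Nothing specified keeps the CAPS-5 rater from side-effect and pill-count information at Visits 3-5, and a printed fixed block of 4 adds a smaller leak; the one-sided Week 8 CAPS-5 contrast could be biased

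*Combined protocol and SAP*

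**What the plan says.** **Randomisation.** The Experimental Design paragraph under Exploratory Outcome Measures states "40 subjects will be randomly assigned to one of two groups", gives the task to pharmacy ("The research pharmacist at the Durham VA will be responsible for randomization of participants in this study") and names a single block size: "a randomized block design will be utilized (4 participants". No varying sizes and no strata are described.

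**Rater.** Secondary Outcome Measures describes CAPS-5 as a structured interview and says "The clinical coordinators in our research group have been trained in the administration of the CAPS".

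**Visible effects.** Potential Risks states: "Side effects exceeding placebo that have occurred in previous clinical trials with DHEA have included mild acne, hirsutism, and decreased HDL levels". It gives no rates. It also allows a return to a previously tolerated dose after side effects, which is a further cue to staff.

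**Side-effect contact.** The Safety Plan has a side-effect scale at each study visit, and the Adverse Events section says "Adverse events will be assessed at all study visits after the screening visit (i.e. Visits 2-5". The Schedule of Events puts CAPS-5 at those same visits and adds adverse-event phone calls at Weeks 3, 5 and 7.

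**Drug accountability.** Potential Difficulties and Limitations plans pill counts without naming who does them. Under Treatment Compliance, for noncompliant subjects, "the PI and/or study coordinator will counsel patients on the importance of study drug compliance and drug accountability".

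**Analysis.** Data Analysis and Statistical Considerations tests CAPS-5 by a 1 df contrast at Week 8, with the alternative that DHEA is lower than placebo.

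The trial is called double-blind throughout. The documents specify no independent rater, no order of assessments within a visit, no concealment of the block size and no check of the blind.

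**The concern.** An interviewer-scored scale is only as blind as its interviewer. If the person scoring CAPS-5 has just seen or recorded new acne or hair growth, or has heard about it by phone, that person has some information about the arm. An expectation that DHEA helps would then move scores in the direction of the one-sided alternative.

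The same bias would enter the planned regression of Week 8 CAPS-5 change on neurosteroid change. That model is first fitted without the treatment variable, and arm is expected to drive steroid levels. Rater expectation could therefore be read as biological support for efficacy.

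The fixed block adds a second path. In a balanced block of known size, recognising one participant says something about the others.

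**Working it through.** **Plan's own figure.** With the dropout in the Experimental Design paragraph ("assuming approximately a 20% drop-out rate"), 40 × (1 − 0.20) = 32, or 16 per arm. This reproduces. (The statistics section attaches a 10% dropout to the same 32; 40 × 0.90 = 36, so that pair does not reproduce. This is a separate matter to reconcile.) The plan gives no CAPS-5 effect size, SD or power.

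**When signs can appear.** All participants take placebo for two weeks and are randomised at Week 2, which is Visit 2. Study-drug signs can therefore inform ratings only at Visits 3, 4 and 5. Before the Week 8 interview there are up to five post-randomisation adverse-event contacts (Weeks 3, 4, 5, 6 and 7).

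**Route 1: the participant's own signs.** Let p1 and p0 be the shares with visible signs on DHEA and placebo. A rater who believes DHEA when signs are seen, and placebo otherwise, is right with probability a = 0.5 + (p1 − p0)/2. If scores differ by s points according to believed arm, bias = (2a − 1) × s = (p1 − p0) × s. All values of p1, p0 and s are assumptions.

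| p1 vs p0 | a | bias, s = 3 | bias, s = 5 |
|---|---|---|---|
| 10% vs 5% | 52.5% | 0.15 | 0.25 |
| 20% vs 5% | 57.5% | 0.45 | 0.75 |
| 30% vs 5% | 62.5% | 0.75 | 1.25 |
| 50% vs 5% | 72.5% | 1.35 | 2.25 |

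**Effect on the test.** Treat the Week 8 contrast as a two-group comparison with 16 per arm, SD 8 to 12 (assumed) and one-sided 0.05 before any multiplicity adjustment. The standard error is SD × √(2/16), that is 2.83 to 4.24 points. With no true effect, the rejection rate runs from 0.054 (bias 0.15, SD 12) to 0.198 (bias 2.25, SD 8).

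**Route 2: the block.** Assume 1:1 allocation, so 2+2 in each of 40/4 = 10 blocks. There are 6 possible sequences.

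- One assignment known: each other member is in the opposite arm with probability 2/3 instead of 1/2. Two alike known: the other two are certain.
- All earlier assignments known: positions 1 to 4 are guessed correctly with probability 1/2, 2/3, 2/3 and 1. The mean is 2.833/4 = 70.8%. Certain assignments are 8 of 24 = 33.3%.
- For comparison, a known block of 6 gives 60.0% (one known) and 68.3% (all earlier known).

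**What the block adds to Route 1.** Enumerating all sign patterns in a block of 4, the accuracies in the table do not change once the participant's own signs are seen. Certainty rises somewhat. With recognition of 30% on DHEA and 0% on placebo, the share known for certain goes from 0.30/2 = 15.0% to 0.30² + 2(0.30)(0.70)/4 = 19.5%. For a participant whose own signs are not yet seen, accuracy rises from 50% to between 51.1% and 57.4% over the four rate pairs.

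**The case against.** The strongest reply is that much of the leak is inferred, and several parts of that reply stand.

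- **Role overlap.** A reader might infer that the same coordinators give the side-effect form, count pills and rate CAPS-5. The documents do not say so. The administrator of the form is not named, and review of side effects is assigned to the PI and study physicians. The gap is that nothing rules the overlap out.
- **Arm-revealing signs.** The acne is called mild and no rates are given. HDL is not among the visit laboratory tests named in Potential Risks. GC/MS steroid assays run only after all participants finish, which is a real safeguard. The signs are possible cues, not identifiers.
- **Every post-baseline visit.** Visit 2 ends the placebo lead-in, so the concern starts at Visit 3.
- **The 71%.** A reader might take this as the rater's accuracy at Week 8. It is the chance of guessing the next assignment when all earlier ones in the block are known for certain and no signs have been seen. It does not describe suspicion at Week 8, when own signs have been seen and block knowledge adds nothing to accuracy. Signs alone would need rates near 47% vs 5% to reach it.
- **Selection at entry.** This needs staff to know earlier allocations, which pharmacy holds, while that block is still open. Signs emerge only after randomised dosing, and lead-in dropouts make enrolment order differ from randomisation order.
- **No way to detect it.** This would be wrong. CAPS-5 interviews are recorded with permission, side-effect forms are kept, and self-report scales such as the BDI-II and PROMIS measures are collected. However, the recordings are reviewed on a sample for interviewer fidelity, with no planned re-scoring, and no analysis of the blind is planned.

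None of this supplies a specified separation between rater and side-effect information.

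**Conclusion.** The point holds as a modest design gap. One fixed block size is printed in the protocol, and an interviewer-scored outcome is collected alongside side effects that exceed placebo, with no stated barrier between them. Rater exposure at Visits 3-5 is the main route; the fixed block is the weaker one.

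The bias in the Week 8 CAPS-5 contrast is about 0.15 to 2.25 points, and the one-sided error about 0.054 to 0.20 instead of 0.05. Both ranges rest on assumed sign rates, rater shift and SD; the documents supply none of these. At the lower sign rates the effect is small.

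It would be too strong to conclude that the blind will fail or that the trial's main result is at risk. The primary outcome is fMRI connectivity, which is not rater-scored, and CAPS-5 is secondary in a 40-person pilot.

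**What to change.** 1. **Blocks.** Use randomly varied block sizes (for example 4 and 6), recorded only in a pharmacy document, and remove the size from the protocol. The gain comes from hiding the boundaries; a larger known block would help little (68.3% against 70.8% in the worst case).
2. **Order and roles.** At Visits 3-5, complete and lock CAPS-5 before the side-effect form, pill count and physical findings are reviewed. This protects only partly, because phone calls and earlier visits also expose staff. Where existing staffing allows, keep CAPS-5 raters off adverse-event and drug-accountability contacts.
3. **Check (optional).** After the Week 8 CAPS-5, record rater and participant arm guesses with reasons, and report them beside the contrast. Use the existing recordings and self-report scales as a comparison. This diagnoses a leak but does not prevent one.

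Cost: a new randomisation list, a fixed visit order and, if adopted, two questions at Week 8. Items 1 and 3 and the visit order need no added staff. Arm sizes could differ by up to 3 if enrolment stops mid-block.
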